**Table 2-1 The PASI scoring system**

Body region	Erythema (E)	Thickening (plaque elevation, induration, I)	Scaling (desquamation) (D)	Area score (based on true area %, A)*
Head (H)**	0=none	0=none	0=none	0 = no involvement
	1=slight	1=slight	1=slight	1 = >0-< 10%
	2=moderate	2=moderate	2=moderate	2 = 10-<30%
	3=severe	3=severe	3=severe	3 = 30-<50%
	4=very severe	4=very severe	4=very severe	4 = 50-<70% 5 = 70-<90% 6 = 90-100%
Trunk, (T)***	0=none	0=none	0=none	0 = no involvement
	1=slight	1=slight	1=slight	1 = >0-< 10%
	2=moderate	2=moderate	2=moderate	2 = 10-<30%
	3=severe	3=severe	3=severe	3 = 30-<50%
	4=very severe	4=very severe	4=very severe	4 = 50-<70% 5 = 70-<90% 6 = 90-100%
Upper limbs (U)	0=none	0=none	0=none	0 = no involvement
	1=slight	1=slight	1=slight	1 = >0-< 10%
	2=moderate	2=moderate	2=moderate	2 = 10-<30%
	3=severe	3=severe	3=severe	3 = 30-<50%
	4=very severe	4=very severe	4=very severe	4 = 50-<70% 5 = 70-<90% 6 = 90-100%
Lower limbs (L)****	0=none	0=none	0=none	0 = no involvement
	1=slight	1=slight	1=slight	1 = >0-< 10%
	2=moderate	2=moderate	2=moderate	2 = 10-<30%
	3=severe	3=severe	3=severe	3 = 30-<50%
	4=very severe	4=very severe	4=very severe	4 = 50-<70% 5 = 70-<90% 6 = 90-100%

Percentage (not score) of body region (not whole body) affected will be entered in the eCRF

\*\*Neck is assessed as part of the Head (H) body region.

\*\*\*Axillae and groin are assessed as part of the Trunk (T) body region.

[figure not shown]
\*\*\*\*Buttocks are assessed as part of the Lower limbs (L) body region.

Because the head and neck, upper limbs, trunk and lower limbs correspond to approximately 10%, 20%, 30% and 40% of the body surface area, respectively, the PASI score is calculated using the formula:

$$\text{PASI} = 0.1(E_H+I_H+D_H)A_H + 0.2(E_U+I_U+D_U)A_U + 0.3(E_T+I_T+D_T)A_T + 0.4(E_L+I_L+D_L)A_L$$

The keys for the letters are provided in [Table 2-1](#).

PASI scores can range from a lower value of 0, corresponding to no signs of psoriasis, up to a theoretic maximum of 72.0. The total score comes from eCRF.

### **Modified Nail Psoriasis Severity Index (mNAPSI)**

The mNAPSI is an instrument to assess psoriatic nail involvement in subjects with PsA and nail psoriasis. It will be collected only in subjects with psoriatic nail involvement. The modifications on the original NAPSI to create the mNAPSI were made by rheumatologists, with dermatologists' input, as a tool for clinical trials. The creators' goal was to develop a tool to assess disease severity and response to treatment in clinical trials, keeping in mind that the assessor in a clinical trial most likely would not be a trained dermatologist. The mNAPSI scores range from 0-130 for all finger nails. The total mNAPSI score will be calculated as the sum of all the scores from available nails.

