8.3.18 Modified Nail Psoriasis Severity Index (mNAPSI)

The mNAPSI is an instrument to assess psoriatic nail involvement in subjects with PsA and nail psoriasis. It will be collected only in subjects with psoriatic nail involvement. The modifications on the original NAPSI to create the mNAPSI were made by rheumatologists, with dermatologists' input, as a tool for clinical trials. The creators' goal was to develop a tool to assess disease severity and response to treatment in clinical trials, keeping in mind that the assessor in a clinical trial most likely would not be a trained dermatologist (Cassell et al 2007). Detailed information is provided in [Appendix 16.7](#).

For the evaluation of the mNAPSI three features or groups of features (onycholysis and oil-drop dyschromia, pitting and crumbling) of each fingernail will be graded on a scale from 0 to 3:

- Onycholysis: Separation of the nail plate from the nail bed. The separated part of the nail is opaque and can have white, yellow, or greenish tinge. If there is a piece of nail missing, estimate where the nail normally would have ended at the end of the nail bed, and count that missing part as involved in onycholysis.
- Oil-drop (salmon patch) dyschromia: Reddish-brown discoloration under the nail plate.

Onycholysis and oil-drop dyschromia are considered together. When looking at the nail, combine the total percentage area of the nail that is affected by either and use that combined total to score the nail.

Table 8-4 Score for percent of nail with onycholysis or oil-drop dyschromia

Score	Percent of nail with onycholysis or oil-drop dyschromia present
0	No onycholysis or oil drop dyschromia present
1	1–10% of the nail has onycholysis or oil-drop dyschromia
2	11–30% of the nail has onycholysis or oil-drop dyschromia
3	> 30% of the nail has onycholysis or oil-drop dyschromia

- Pitting: Small, sharply defined depressions in the nail surface. Pits are discrete abnormalities (“ice-pick-like”). If there is nail plate crumbling that is confluent with pits, do not score for pits. If the pits are separate from crumbling, they may be scored regardless of whether crumbling is present or not.

Table 8-5 Score for number of pits

Score	Number of pits
0	0
1	1–10
2	11–49
3	> 50

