- Nail plate crumbling: Crumbling or fragmentation of friable nail plate which may be associated with confluent pitting. Crumbling involves alteration of the nail plate surface. Horizontal ridging of the nail, “wave-like” appearance, and horizontal lines are all features of crumbling.

Table 8-6 Score for percent of nail with crumbling present

[figure not shown]
Score	Percent of nail with crumbling present
0	No crumbling
1	1–25% of the nail has crumbling
2	26–50% of the nail has crumbling
3	> 50% of the nail has crumbling

The next 4 abnormalities (leukonychia, splinter hemorrhages, hyperkeratosis, and red spots in the lunula) are scored only as either present or absent for each fingernail. A score of 1 indicates present and a score of zero indicates not present.

1. Leukonychia: White spots in the nail plate due to psoriasis in the mid matrix. Leukonychia are just color changes. If it appears that there is depression or irregularity to the nail surface, this may be pitting or crumbling, not leukonychia. If the leukonychia is adjacent to or confluent with crumbling or pits, it is counted as part of the crumbling or pitting and not as a separate abnormality.
2. Splinter hemorrhages: Small, longitudinal, linear, dark brown hemorrhage under the fingernail.
3. Nail bed hyperkeratosis: Thickened keratin in the nail bed.
4. Red spots in the lunula: Small pink or red macules in the lunula.

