12.5 Analysis of secondary endpoints

12.5.1 Efficacy [REDACTED] endpoint(s)

Efficacy variables

The secondary efficacy variables are listed below. Secondary efficacy variables will be analyzed using the FAS population unless otherwise specified.

- ACR20 response at Week 16
- Minimal disease activity (MDA) response at Week 16

- PASI90 response for psoriasis subset at Week 16
- Change from baseline in PASDAS score at Week 16
- Change from baseline in HAQ-DI[©] score at Week 16
- Change from baseline in SF36-PCS at Week 16
- Change from baseline in FACIT-Fatigue score at Week 16
- Change from baseline in mNAPSI for nail subset at Week 16
- Resolution of dactylitis for dactylitis subset at Week 16
- Resolution of enthesitis for enthesitis subset at Week 16

Testing strategy

- The following hypotheses will be included in the testing strategy, and type-I-errors will be set such that a family-wise type-I-error of 5% is kept:

Primary objectives

[figure not shown]
- H₁: i.v. secukinumab regimen is not different to placebo regimen with respect to ACR50 response at Week 16

Secondary objectives

- H₂: i.v. secukinumab regimen is not different to placebo regimen with respect to ACR20 response at Week 16
- H₃: i.v. secukinumab regimen is not different to placebo regimen with respect to MDA response at Week 16
- H₄: i.v. secukinumab regimen is not different to placebo regimen with respect to PASI90 response at Week 16 in the subset of subjects who have $\geq 3\%$ skin involvement with psoriasis at baseline
- H₅: i.v. secukinumab regimen is not different to placebo regimen with respect to the change from baseline in PASDAS at Week 16
- H₆: i.v. secukinumab regimen is not different to placebo regimen with respect to the change from baseline in HAQ-DI[©] score at Week 16
- H₇: i.v. secukinumab regimen is not different to placebo regimen with respect to change from baseline in SF36-PCS score at Week 16
- H₈: i.v. secukinumab regimen is not different to placebo regimen with respect to change from baseline in FACIT-Fatigue score at Week 16
- H₉: i.v. secukinumab regimen is not different to placebo regimen with respect to change from baseline in mNAPSI score at Week 16 in the subset of subjects with PsA and nail psoriasis at BSL.
- H₁₀: i.v. secukinumab regimen is not different to placebo regimen with respect to resolution of dactylitis response at Week 16 in the subset of subjects who have dactylitis at BSL.

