### Psoriatic Arthritis Disease Activity Score (PASDAS)

PASDAS is a new composite measure developed to access disease activity in Psoriasis (GRACE Project) ([Helliwell 2012](#)). It is calculated by utilizing seven measures; the seven components are: Patient reported measures (excluding mental component summary score (MCS) of the medical outcomes survey Short Form-36 (SF-36-PCS)), skin, peripheral joint counts (Tender and Swollen joint counts), Dactylitis (LDI), Enthesitis (LEI), acute phase response (CRP) and Patient & Physician global VAS scores.

$$\begin{aligned} \text{PASDAS} = & (((0.18 \times \sqrt{\text{Physician global VAS}}) \\ & + (0.159 \times \sqrt{\text{Patient global VAS}}) \\ & - (0.253 \times \sqrt{\text{SF36-PCS}}) \\ & + (0.101 \times \ln(\text{Swollen joint count} + 1)) \\ & + (0.048 \times \ln(\text{Tender joint count} + 1)) \\ & + (0.23 \times \ln(\text{Leeds Enthesitis Count} + 1)) \\ & + (0.377 \times \ln(\text{Dactylitis count} + 1)) \\ & + (0.102 \times \ln(\text{CRP} + 1)) + 2) * 1.5. \end{aligned}$$

If any component measurement is missing, PASDAS will be missing. The patient global VAS defined in the PASDAS score is “VAS for PASDAS assessment” which measures patient’s global assessment of PSORIASIS and ARTHRITIS disease activity. The Physician global VAS is the Physician’s global assessment of PsA disease activity. Tender Dactylitis count is from “Leeds Dactylitis Instrument” CRF page with “Was dactylitis present?” = “Yes” and “Tender/non-tender” = “Tender”.

66-swollen / 68-tender joint counts for PASDAS assessment:

There are only 66 swollen and 68 tender joint counts which will be used for PASDAS assessment. That is the 10 joints in CRF: CMC1, DIP2 (FOOT), DIP3 (FOOT), DIP4 (FOOT), and (DIP5 (FOOT) both left and right, should not be counted in the swollen/tender joint count in PASDAS formula.

If the number of joints for which data were available (e.g., T) is less than 66/68 for the swollen/tender joint assessment, the number of swollen/tender joints (e.g., t) will be scaled up proportionately (i.e.,  $66*t/T$  or  $68*t/T$  for swollen or tender joint count).

[figure not shown]

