### FACIT - Fatigue

[figure not shown]
The Functional Assessment of Chronic Illness Therapy – Fatigue (FACIT-Fatigue©) is a 13-item questionnaire that assesses self-reported fatigue and its impact upon daily activities and function.

Subjects respond to each item on a 5-point Likert-type scale (0 = not at all; 1 = a little bit; 2 = somewhat; 3 = quite a bit; 4 = very much) based on their experience of fatigue during the past 2 weeks. The scale score is computed by summing the item scores, after reversing those items that are worded in the negative direction. Numbering the questions from 1 to 13, it is evident that questions 7 and 8 are worded in the positive direction (4 indicates a desirable response) and all other questions are worded in the negative directions (4 indicates an undesirable response). Thus, it is necessary to reverse the responses for all but questions 7 and 8 (i.e. original response of 0 gets mapped to 4, 1=3, 2=2, 3=1, and 4=0) for scoring purposes.

When there are missing item scores, the subscale score was computed by summing the non-missing item scores, multiplying by 13 (the total number of items in the scale) and dividing by the number of non-missing items (i.e. normalizing the results). The latter rule applied only when at least half of the items (seven or more) are non-missing.

FACIT Fatigue subscale scores range from 0 to 52, where higher scores represent less fatigue ([Cella D et al., 2004](#)).

[figure not shown]

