**Table 3-3 Summary of power for continuous secondary endpoints**

Endpoint (Week 16)	Placebo Mean change from baseline	Secukinumab with 150 mg SC Loading			Secukinumab with 300 mg SC Loading		
		Mean change from baseline	Common standard deviation	Power N=190/ arm	Mean change from baseline	Common standard deviation	Power N=190/ arm
HAQ-DI	-0.21	-0.44	0.507	99%	-0.55	0.508	99%

mNAPSI	-2.49	-9.31	9.503	99%	-9.18	9.503	99%
FACIT	1.98	6.18	9.303	99%	6.8	9.303	99%
SF36-PCS	1.83	6.3	7.304	99%	7.62	7.33	99%
PASDAS	-0.91	-2.02	1.359	99%	-2.37	1.361	99%

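### The mNAPSI total sums available nails without rescaling, so a diseased nail left unassessed at a later visit is scored as clear and recorded as improvement

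*SAP*

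**What the plan says.** SAP section 2.5.1 gives the scale and the rule together: "The mNAPSI scores range from 0-130 for all finger nails", and then "The total mNAPSI score will be calculated as the sum of all the scores from available nails". Nothing follows on a nail that was not assessed. Protocol section 8.3.18 and Appendix 7 cover only the scoring of single nails. Their one instruction on missing tissue concerns a missing piece of a nail that is being scored, which is counted as onycholysis.

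Other scores in the SAP are corrected for missing parts:

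- **PASDAS joint counts:** with fewer than 66 or 68 joints available, the count "will be scaled up proportionately".
- **FACIT-Fatigue:** prorated by "multiplying by 13 (the total number of items in the scale) and dividing by the number of non-missing items", provided at least seven items are present.
- **HAQ-DI:** divided by the number of categories answered, with at least six of eight required.

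The endpoint in Protocol section 12.5.1 is "Change from baseline in mNAPSI for nail subset at Week 16", tested as H9. SAP section 1 limits the SAP to the final database lock and says that Week 16 and testing-hierarchy analyses are not redone. In SAP Table 4-1, mNAPSI (Group 8) has analysis windows up to Week 52.

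**The concern.** In a plain sum, a nail that was not looked at is indistinguishable from a nail that was looked at and found clear. Zero is the best score a nail can have, so an incomplete follow-up assessment makes the patient look better.

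Later steps do not repair this. The missing-data rules in SAP section 2.5.3, and the missing-at-random argument for the repeated-measures model in Protocol sections 12.4.3 and 12.5.1, act on missing totals. A partial total is present and simply too low. A partial baseline also enters the model as a covariate with the wrong value.

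At stake are the mNAPSI changes reported over time by treatment sequence. Because these are within-group changes, equal missingness in the two sequences would not protect them.

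**Working it through.** **1. The plan's range.** Protocol section 8.3.18 grades three features or groups of features, "of each fingernail will be graded on a scale from 0 to 3". It scores four further abnormalities as present or absent: "A score of 1 indicates present and a score of zero indicates not present".

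- Maximum per nail: 3 × 3 + 4 × 1 = 13.
- Ten fingernails: 10 × 13 = 130, which agrees with the SAP. A full-scale total therefore needs all ten nails.

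**2. What the rule does to one nail.** Let the nail score *s* at baseline, and let *u* be what it would have scored at the later visit. The table shows its contribution to change from baseline.

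| Nail assessed at | True contribution | Recorded contribution | Error |
|---|---|---|---|
| both visits | u − s | u − s | 0 |
| baseline only | u − s | −s | −u |
| later visit only | u − s | u | +s |
| neither visit | u − s | 0 | s − u |

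In the second row the recorded improvement is *s*, of which *u* is false. If the nail had not changed (u = s), all of it is false. If it had really cleared (u = 0), none is. In the third row the recorded worsening is *u*, and the error runs the other way.

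**3. Size for one patient.** The documents give no baseline mNAPSI, so totals of 15, 20 and 30 are assumptions, with severity spread evenly, no true change and one nail missed later.

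| Assumed baseline | Per nail | Raw total, 9 nails | Recorded change | Prorated total (× 10/9) | Prorated change |
|---|---|---|---|---|---|
| 15 | 1.5 | 13.5 | −1.5 | 15 | 0 |
| 20 | 2.0 | 18 | −2.0 | 20 | 0 |
| 30 | 3.0 | 27 | −3.0 | 30 | 0 |

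The bound is 13 points, for a nail at its worst on every feature.

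**4. Size for a group.** Shift in mean change = proportion of subjects affected × points lost. With 5% of subjects missing one 2-point nail, the shift is 0.05 × 2 = 0.1 point. Between arms only the difference in proportions counts:

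- equal proportions: 0
- 5 percentage points apart, 2 points lost: 0.05 × 2 = 0.1
- 10 percentage points apart, 4 points lost: 0.10 × 4 = 0.4

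The proportions are assumptions, since neither document says how often nails go unassessed.

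**5. Power.** SAP Table 3-3 plans mean changes of −2.49 (placebo), −9.31 (150 mg) and −9.18 (300 mg), with SD 9.503. The differences are −9.31 + 2.49 = −6.82 and −9.18 + 2.49 = −6.69. With 190 per arm and two-sided 5%, power exceeds 0.999 for both, consistent with the 99% shown. It is still about 0.99 if only 40% of subjects (76 per arm, an assumption) have nail disease. Power is not affected by this point.

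**The case against.** Several arguments limit the point, and most of them stand.

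- **The Week 16 test.** A reader might infer that H9 is biased. The documents do not support that. This SAP covers the final lock, its section 2.11 says the 16-week analysis is already done, and the protocol's mNAPSI sections contain no rule on available nails.
- **The benchmark.** A reader might set a 2-point error against the planned difference of 6.82 and call it 29% (2 / 6.82). That divides one patient's error by a difference between group means. It is also a Week 16 contrast with placebo, whereas after Week 16 everyone receives secukinumab and the SAP's repeated-measures code (section 4.2.1.2) has no treatment term.
- **The direction.** A reader might infer a consistent bias towards improvement. The direction reverses for a nail missed at baseline. A nail clear at baseline and missed later adds nothing to the recorded change, and so does a nail absent at every visit.
- **The comparison with other scores.** mNAPSI is not the only score without such a rule. The LEI and LDI descriptions in SAP section 2.5.1 also state none for unassessed sites or digits, and the joint scaling is stated for PASDAS only.
- **The remedy.** Proration assumes that the missing nail resembles the others. For a nail absent throughout, it multiplies the observed change by 10/9.

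None of this removes the basic fault: the stated rule gives an incomplete assessment a valid-looking total that is too low whenever the missing nail is diseased.

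**Conclusion.** The point holds for the long-term mNAPSI summaries, which this SAP directly governs. An affected patient's total is too low by the unassessed nail's score: between 0 and 13 points, and about 1.5 to 3 points under the assumed baseline totals with unchanged severity. The sign of the error in the change score depends on which visit is incomplete.

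At group level the effect is probably small, about 0.1 point in the 5% illustration, but it cannot be settled without the frequency of partial assessments. The documents do not support saying that H9 was affected or that the treatment effect is overstated. The correction is worth making because it is cheap and brings mNAPSI into line with how the same SAP treats PASDAS joint counts, FACIT-Fatigue and HAQ-DI.

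**What to change.** In SAP section 2.5.1, replace the summation sentence with: *The mNAPSI total is the sum over assessed fingernails × 10 / number of fingernails assessed, if at least five of the ten are assessed; otherwise it is missing.* The one-half threshold follows the FACIT-Fatigue rule.

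In addition:

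- For subjects with a nail absent at any visit, compute change over the nails assessed at both baseline and that visit, as a check on proration.
- Report the number of partial nail assessments by visit and treatment sequence. If there are none, no result changes.
- State which rule the Week 16 analysis used. If it was the raw sum, show the Week 16 mNAPSI result under the revised rule as a sensitivity analysis.

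The cost is one sentence, one line of derivation code and a small table, plus the sensitivity run if needed. The SAP's document history places it before database lock. The downsides are the assumption that a missing nail resembles the assessed ones, and scoring that may differ from the Week 16 report, which should be stated wherever the two are shown together.

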### Psoriatic Arthritis Disease Activity Score (PASDAS)

PASDAS is a new composite measure developed to access disease activity in Psoriasis (GRACE Project) ([Helliwell 2012](#)). It is calculated by utilizing seven measures; the seven components are: Patient reported measures (excluding mental component summary score (MCS) of the medical outcomes survey Short Form-36 (SF-36-PCS)), skin, peripheral joint counts (Tender and Swollen joint counts), Dactylitis (LDI), Enthesitis (LEI), acute phase response (CRP) and Patient & Physician global VAS scores.

$$\begin{aligned} \text{PASDAS} = & (((0.18 \times \sqrt{\text{Physician global VAS}}) \\ & + (0.159 \times \sqrt{\text{Patient global VAS}}) \\ & - (0.253 \times \sqrt{\text{SF36-PCS}}) \\ & + (0.101 \times \ln(\text{Swollen joint count} + 1)) \\ & + (0.048 \times \ln(\text{Tender joint count} + 1)) \\ & + (0.23 \times \ln(\text{Leeds Enthesitis Count} + 1)) \\ & + (0.377 \times \ln(\text{Dactylitis count} + 1)) \\ & + (0.102 \times \ln(\text{CRP} + 1)) + 2) * 1.5. \end{aligned}$$

If any component measurement is missing, PASDAS will be missing. The patient global VAS defined in the PASDAS score is “VAS for PASDAS assessment” which measures patient’s global assessment of PSORIASIS and ARTHRITIS disease activity. The Physician global VAS is the Physician’s global assessment of PsA disease activity. Tender Dactylitis count is from “Leeds Dactylitis Instrument” CRF page with “Was dactylitis present?” = “Yes” and “Tender/non-tender” = “Tender”.

66-swollen / 68-tender joint counts for PASDAS assessment:

There are only 66 swollen and 68 tender joint counts which will be used for PASDAS assessment. That is the 10 joints in CRF: CMC1, DIP2 (FOOT), DIP3 (FOOT), DIP4 (FOOT), and (DIP5 (FOOT) both left and right, should not be counted in the swollen/tender joint count in PASDAS formula.

If the number of joints for which data were available (e.g., T) is less than 66/68 for the swollen/tender joint assessment, the number of swollen/tender joints (e.g., t) will be scaled up proportionately (i.e.,  $66*t/T$  or  $68*t/T$  for swollen or tender joint count).

[figure not shown]
#### VAS for PASDAS assessment:

Global Disease Activity: The patient’s assessment of PSORIASIS and ARTHRITIS will be performed using 100 mm VAS ranging from “Excellent” to “Poor” after the question *“Considering all the ways PSORIASIS and ARTHRITIS affects you, please indicate with a vertical mark (|) through the horizontal line how well you are doing over the past week”*.

